### **4.1 Target Accrual**

**Main Cohort:** Up to 44 patients are expected to be needed to estimate the biologic impact of this regimen and establish a preliminary estimate of efficacy. This number includes the following tiers of the dose-escalation of IFN $\alpha$  (3+3 design with 0, 5 MU/M $^2$ , 10 MU/M $^2$ , and 20 MU/M $^2$ ). Once an MTD is established, subsequent patients (n = 10) will receive rintatolimod + IFN $\alpha$  (at the MTD or, in the absence of an MTD, at 20 MU/M $^2$  IFN $\alpha$ ) as well as standard of care. Total accrual time is expected to take 36 months.

**Expansion Cohort:** In addition, we will accrue a maximum of 20 patients on Expansion Cohort, who will receive rintatolimod and best available standard care.

Roswell Park Protocol No.: I-659920

## 5 LOCAL AND STUDY-WIDE RECRUITMENT METHODS

### 5.1 Recruitment

Subjects will be recruited from Roswell Park and our affiliate practices, and University at Buffalo-affiliated hospital systems. Recruitment efforts will focus on patients with initial signs of COVID-19 who would be offered enrollment as soon as feasible. In addition, asymptomatic patients with contact (e.g., household member or health care-associated exposure) with COVID-19 will be monitored for development of symptoms or signs of COVID-19 that would result in nasopharyngeal swab PCR testing: Roswell Park is a New York State-designated regional laboratory for COVID-19 PCR-based testing with same or next day reporting of results.

Men and women will be recruited, with age, race, and socioeconomic status expected to reflect the general Roswell Park patient population.

## 6 MULTI-SITE RESEARCH

The study will be opened at Roswell Park first to obtain preliminary safety data and establish feasibility, but we may prospectively partner with other cancer centers as study sites in regions with established community-based transmission of COVID-19.

## 7 STUDY TIMELINES

Main Cohort: A maximum of 44 evaluable participants will be enrolled to the study over up to 36-months. Patients will be followed until Day 30 after initiation of the study regimen.

Expansion Cohort: A maximum of 20 evaluable participants will be enrolled to the study over up to 36-months. Patients will be followed until Day 30 after initiation of the study regimen.

Enrollment in the Main Cohort and Expansion Cohort will be done concurrently. If a patient is eligible for enrollment in both the Main and Expansion Cohort and is willing to be enrolled in either cohort, priority will be given to the Main Cohort.

## 8 STUDY ENDPOINTS

### 8.1 Primary Endpoints

- The primary safety endpoints are frequency of grade 3 or 4 AEs considered to be probably or definitely related to the treatment regimen.
- Evaluate kinetics of viral load expressed as Ct values in nasopharyngeal swab samples in the course of treatment and Days 7 and 14. (40)

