## **16 MEASUREMENT OF EFFECT**

### **16.1 Primary Endpoints**

- The **primary safety** endpoints are frequency of grade 3 or 4 AEs considered to be possibly, probably, or definitely related to the treatment regimen.
- Evaluate kinetics of viral load in nasopharyngeal swabs based on quantitative PCR in the course of treatment and Days 7, and 14.

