## **19 STATISTICAL PLAN**

### **19.1 Study Design/Endpoints**

This is prospective Phase I/IIa trial basket trial of i.v. rintatolimod administered with or without i.v. IFN $\alpha$  (INTRON $\circledR$  A) in two cohorts of patients: Main Cohort and Expansion Cohort. Only Main Cohort subjects will participate in the Phase I 3+3 portion of this study. The Expansion

Roswell Park Protocol No.: I-659920

Cohort will consist of rintatolimod without IFN $\alpha$ . Neither cohort is randomized. The kinetics of nasopharyngeal viral load will be assessed based on baseline values and on treatment and EOT values. In the Expansion Cohort, the kinetics of nasopharyngeal viral load will be compared with historical controls consisting of Roswell Park patients with COVID-19 of varying severity. All patients will receive best available standard of care in addition to study drug regimens.

**Phase I.** The Phase I component of the protocol consists of a 3+3 design with four dose levels of IFN $\alpha$  (0, 5 MU/M, 10 MU/M and 20 MU/M ) and fixed dose rintatolimod (200 mg per day) administered on Days 1 and 3. The sample size for the Phase I trial may range from n=3 to 24.

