### **Primary Endpoint**

- The primary safety endpoint is the frequency of grade 3 or 4 AEs considered to be possibly, probably, or definitely related to the treatment regimen.

**Phase IIa.** The Phase IIa component of the trial is designed to be a single arm trial of IFN $\alpha$  (at MTD, if reached, otherwise at 20 MU/M) + rintatolimod along with the best available standard of care. Using each patient's baseline nasopharyngeal viral load, we will evaluate to what extent the study regimen reduces viral load relative historical institutional benchmarks. The sample size will be n=10.

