### **Primary Endpoint**

- Evaluate kinetics of viral load expressed as Ct values in nasopharyngeal swab samples over time measured at baseline (day 0), Days 3 (last day of treatment), 7, and 14 (40). The primary endpoint will be the area under the Ct curve (AUC).

The primary Phase IIa safety endpoint is the frequency of grade 3 or 4 AEs considered to be probably or definitely related to the treatment regimen.

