### **Correlative Endpoints**

- Determine the kinetics of changes of the immune subsets and circulating inflammatory mediators (including CRP, cytokines, chemokines, interferons) in peripheral blood in the course of treatment at baseline (Day 0), Days 3, 7, and 14. Plasma and PBMCs will be cryopreserved for future exploratory studies, including the assessment of intracellular signaling and TCR and BCR repertoires as correlates of response to the study regimen.
- Induction of known mediators of antiviral immunity that include (myxovirus resistance gene, MxA; protein Kinase R (PKR); oligoadenylate synthetase-2 (OAS2); RNase-L, IFN-stimulated gene-15 (ISG15); IFN-induced proteins with tetratricopeptide repeats (IFIT1) and IFN-inducible transmembrane protein 3 (IFITM3), TLR3, RIG-I, MDA5, IRF3, IRF7, in nasopharyngeal swabs material and blood cells of patients on all tiers of treatment. Expression of ACE2 (receptor for SARS-CoV-2 entry) and potentially other genes involved in SARS-CoV-2 infection will be tested in nasopharyngeal samples.

Roswell Park Protocol No.: I-659920

All subjects meeting the eligibility criteria who signed a consent form and receive rintatolimod control will be considered evaluable for efficacy analysis. Safety analysis will be performed on all patients who have signed a consent form and received at least one dose of study medication.

The primary efficacy analysis of the Phase IIa component of the study will be on the intention to treat (ITT) population, which will include all patients who have signed a consent form and undergone randomization, according to the treatment group to which they were allocated.

All data collected will be summarized and presented. Continuous variables will be described as the mean, median, standard deviation, and range of the observations. Categorical data will be described with contingency tables including frequency and percentage. Individual patient listings will be generated and presented.

Statistical descriptions and analyses will be carried out using SAS statistical analysis software version 9.4 or higher (SAS Institute, Inc., Cary, North Carolina, USA).

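### The primary safety endpoint has two attribution rules in Sections 8.1 and 16.1, no clear rule for the Expansion Cohort, and a grade range that literally leaves out related deaths

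*Combined protocol and SAP*

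**What the plan says.** The combined protocol and SAP defines the primary safety endpoint in four places.

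- Section 8.1, with no phase or cohort named: "The primary safety endpoints are frequency of grade 3 or 4 AEs considered to be probably or definitely related to the treatment regimen".
- Section 16.1, also unlabelled, says that the primary safety "endpoints are frequency of grade 3 or 4 AEs considered to be possibly, probably, or definitely related to the treatment regimen".
- Section 19.1, under Phase I: "The primary safety endpoint is the frequency of grade 3 or 4 AEs considered to be possibly, probably, or definitely related".
- Section 19.1, under Phase IIa: "The primary Phase IIa safety endpoint is the frequency of grade 3 or 4 AEs considered to be probably or definitely related".

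Three further statements decide who falls under which rule. Section 19.1 limits dose escalation to one cohort: "Only Main Cohort subjects will participate in the Phase I 3+3 portion of this study". It then ties Phase IIa to interferon plus rintatolimod, with 10 patients: "The Phase IIa component of the trial is designed to be a single arm trial of IFN". Section 4.1 adds a rintatolimod-only group: "we will accrue a maximum of 20 patients on Expansion Cohort, who will receive rintatolimod and best available standard care". Section 19.1 nonetheless puts every treated patient in the safety analysis: "Safety analysis will be performed on all patients who have signed a consent form and received at least one dose of study medication".

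**The concern.** A primary endpoint should have one definition for each group of patients it covers. Here two sections with the same heading give different definitions, and the difference is whether possibly related events count.

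That category matters in this trial. Under Section 17.6.1 an event is probable only if factors such as the patient's clinical state cannot reasonably explain it; an event they could have produced is possible. Section 10.2.2 acknowledges that COVID-19 and treatment toxicity overlap. Sections 2.2 and 2.3 give worse inflammatory lung injury as a reason for making safety a primary endpoint. In a patient with COVID-19, that harm could well be rated possible and drop out under the narrower rule.

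At stake is which rate is reported as the primary safety result. The trial is not randomized, and as written the choice could be made after the data are seen. Separately, a safety rate limited to grades 3 and 4 omits the most severe related outcome.

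**Working it through.** The plan gives no target rate, power or threshold for this endpoint, so there is no figure to reproduce. The check sets the texts side by side and then sizes the difference.

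**Step 1. The four definitions**

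| Place | Phase or cohort named | Grades | Attribution counted |
|---|---|---|---|
| 8.1 | none | 3, 4 | probable, definite |
| 16.1 | none | 3, 4 | possible, probable, definite |
| 19.1, Phase I | Phase I | 3, 4 | possible, probable, definite |
| 19.1, Phase IIa | Phase IIa | 3, 4 | probable, definite |

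**Step 2. Which rule reaches which patients**

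| Group | n (source) | 8.1 | 16.1 | 19.1 | Result |
|---|---|---|---|---|---|
| Main Cohort, Phase I | 3 to 24 (19.1) | narrow | broad | broad | 8.1 disagrees |
| Main Cohort, Phase IIa | 10 (19.1) | narrow | broad | narrow | 16.1 disagrees |
| Expansion Cohort | up to 20 (4.1) | narrow | broad | none named | unresolved |

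The Expansion Cohort is barred from Phase I and receives no interferon, so it does not meet 19.1's description of Phase IIa. The unlabelled statements in 8.1 and 16.1 do reach it, but they disagree.

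**Step 3. Size of the attribution difference**

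Assume that the unit is the patient. The two rules differ only for a patient whose sole related grade 3-4 event is rated possible. Each such patient changes the rate by 1/n:

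- Phase IIa: 1/10 = 10 points.
- Expansion Cohort at its maximum: 1/20 = 5 points.
- Phase I: 1/3 = 33.3 points at the smallest size, 1/24 = 4.2 points at the largest.

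For illustration, assume k such patients and no other qualifying events. The narrower rule then reports 0/n and the broader rule k/n. Exact (Clopper-Pearson) two-sided 95% intervals are in brackets.

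| Group | Narrow rule | Broad rule, k = 1 | Broad rule, k = 3 |
|---|---|---|---|
| Phase IIa, n = 10 | 0% (0 to 30.8) | 10% (0.3 to 44.5) | 30% (6.7 to 65.2) |
| Expansion, n = 20 | 0% (0 to 16.8) | 5% (0.1 to 24.9) | 15% (3.2 to 37.9) |

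The documents give no basis for predicting k. With k = 0 the rules agree.

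**Step 4. Grade 5**

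None of the four definitions extends above grade 4. Section 10.2.3 calls treatment-related deaths grade 5 when it describes an earlier interferon trial. That is not a rule for this trial, but it shows that the document's own grading places death above grade 4. Read literally, a related death is not counted.

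**The case against.** The strongest reply is that Section 19.1, the statistical plan, already assigns one rule to each phase, that 8.1 matches its Phase IIa wording and 16.1 its Phase I wording, and that only labels are missing. For the Main Cohort this largely stands: a statistician following 19.1 would know what to do. It does not correct 8.1 and 16.1, neither of which mentions the split. Nor does it settle the Expansion Cohort. Exclusion from Phase I points towards the Phase IIa rule, but Phase IIa is defined by a drug this cohort does not receive.

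A second reply is that little can be hidden. Both routine reporting tables in Section 17.6.2 collect grade 3 and 4 events of every attribution, and 19.1 promises individual patient listings. If those listings show attribution, either rate can be recovered. That stands, and it narrows the problem to which rate is called primary.

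A third is that deaths have their own routes: SAE reporting (Sections 17.7 and 17.7.1) and death within 30 days as a secondary endpoint (Sections 8.2, 16.2 and 19.1). That also stands. A reader might infer that fatal toxicity would go unrecorded; the documents do not support this. The gap is only in the primary safety rate.

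A reader might also infer that the conflict undermines dose escalation. It does not. Section 19.2.1 escalates on DLTs, which under Section 10.2.2 already include possibly related events.

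**Conclusion.** The point holds as an inconsistency in a primary endpoint with a descriptive effect, and it should be fixed. Three things are established from the text: 8.1 and 16.1 conflict and neither carries a phase label; no rule is clearly assigned to the Expansion Cohort; and related deaths fall outside the literal grade range.

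No test, sample size or escalation decision depends on this endpoint, and data safety monitoring committee review (Sections 19.7 and 20) does not turn on its wording. It would be too strong to say that the Main Cohort has no usable safety definition, or that the narrower Phase IIa rule is itself an error; 19.1 states that rule explicitly and may intend it.

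The sizes in points rest on counting patients. The documents speak of the frequency of AEs without saying whether patients or events are counted; the percentages that 19.1 promises for categorical data suggest patients. The number of patients affected is unknown, so the actual shift may be zero.

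**What to change.** 1. Make 8.1 and 16.1 match 19.1 by stating the attribution rule for each phase. One common rule throughout would also remove the conflict.
2. Name the rule for the Expansion Cohort in all three sections.
3. In every statement of the endpoint, replace the grade 3 or 4 range with grade 3 or higher, so that treatment-related deaths count.
4. State that the unit is the patient: the number and proportion with at least one such event.
5. Report two rates side by side, by phase and cohort: one counting possible, probable and definite attribution, the other only probable and definite. Say in advance which is primary for each group.

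The cost is a wording amendment; grade, attribution and deaths are already collected. The drawback is that the broader rate will include some events caused by COVID-19, which is why the narrower rate should stand beside it.

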### 8.2 Secondary Endpoints\*

- Clinical efficacy will be assessed by the frequency of these complications: (i) progression of infection requiring hospitalization; (ii) respiratory failure requiring mechanical ventilation; and (iii) death within 30 days.

Although the data on outcomes in patients with COVID-19 and cancer are limited, based on the Chinese experience, approximately 40% are expected to have the composite endpoint of respiratory failure requiring mechanical ventilation or death (1). We note the limitations of this

Roswell Park Protocol No.: I-659920

estimate regarding small numbers of patients with cancer and heterogeneity in cancer types and co-morbidities, including older age, smoking, and lung disease (41). If present, acute respiratory distress syndrome (ARDS) will be graded by Berlin criteria (42), which include 3 mutually exclusive categories of ARDS based on degree of hypoxemia: mild ( $200 \text{ mm Hg} < \text{PaO}_2/\text{FIO}_2 \leq 300 \text{ mm Hg}$ ), moderate ( $100 \text{ mm Hg} < \text{PaO}_2/\text{FIO}_2 \leq 200 \text{ mm Hg}$ ), and severe ( $\text{PaO}_2/\text{FIO}_2 \leq 100 \text{ mm Hg}$ ). The degree of ARDS is has been validated as a predictor of mortality in patients with respiratory failure. The Berlin criteria require 5cm H2O as the minimum level of PEEP delivered by a ventilator or CPAP for diagnosing ARDS; if PEEP is not administered, then ARDS cannot be diagnosed. In addition, the Berlin criteria require excluding hydrostatic pulmonary edema by clinical judgement or with echocardiograph as a cause of respiratory failure. Although the study is not powered for the clinical endpoint, in case that any of the elements of the clinical efficacy endpoint will reach statistical difference between arms, such clinical endpoint will be considered as an overruling endpoint of efficacy

- Evaluate kinetics of viral load as Ct values in peripheral blood in the course of treatment and Days 7 and 14 (40).
- Determine the kinetics of changes of the immune subsets and circulating inflammatory mediators (including CRP, cytokines, chemokines, interferons) in peripheral blood in the course of treatment. Plasma and PBMCs will be cryopreserved for future exploratory studies, including the assessment of intracellular signaling and TCR and BCR repertoires as correlates of response to the study regimen.
- Determine the induction of known mediators of antiviral immunity that include (myxovirus resistance gene, MxA; protein Kinase R (PKR); oligoadenylate synthetase-2 (OAS2); RNase-L, IFN-stimulated gene-15 (ISG15); IFN-induced proteins with tetratricopeptide repeats (IFIT1) and IFN-inducible transmembrane protein 3 (IFITM3), TLR3, RIG-I, MDA5, IRF3, IRF7, in nasopharyngeal swab material and blood cells of patients on all tiers of treatment. Expression of ACE2 (receptor for SARS-CoV-2 entry) and potentially other genes involved in SARS-CoV-2 infection will be tested in nasopharyngeal samples.

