### **Secondary Endpoints**

- Clinical efficacy will be assessed by the frequency of these complications: (i) progression of infection requiring hospitalization; (ii) respiratory failure requiring mechanical ventilation; (iii) death within 30 days and (iv) Time to a Ct value of non-detectable.

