### 19.2.2 Efficacy

In order to compare the AUC between rintatolimod versus historical institutional benchmarks we will use the highly efficient approach proposed by Chandrasekhar et al (48). Ct values measured at baseline (Day 0), Days 3, 7 and 14 will be used to measure the AUC using a standard trapezoidal rule where the AUC for the  $i$ th subject in group  $k$  ( $k=1$  for rintatolimod and  $k=2$  for control) as  $AUC_{jk} = \sum_{i=1}^m c_j Y_{ijk}$  where  $t_1 = 0, t_2 = 3, t_3 = 7, t_4 = 14, t_5 = 30$ ,  $m = 5$ , the  $Y_{ijk}$ 's denote the corresponding Ct values per subject at the respective time points and

$$c_j = \begin{cases} \frac{t_{j+1} - t_j}{2}, & j = 1 \\ \frac{t_j - t_{j-1}}{2}, & j = m \\ \frac{t_{j+1} - t_{j-1}}{2}, & \text{otherwise} \end{cases}$$

If a Ct value is  $>40$  it will be considered right censored for the purpose of this analysis, which corresponds to a non-detectable level. We can re-express this formulation using a linear mixed model with details given exactly as in Chandrasekhar et al. (48). A large AUC value for a respective subject is a measure of treatment efficacy as compared to a subject with a lower AUC

Roswell Park Protocol No.: I-659920

value. The primary test of efficacy will be H0:  $AUC=130$  (log2 copies) x day versus H1:  $AUC>130$  (log2 copies) x day.

The secondary clinical efficacy endpoints of (i) progression of infection requiring hospitalization in patients who were not inpatients at study entry; (ii) respiratory failure requiring mechanical ventilation; and (iii) death within 30 days will be compared using Fisher's exact test. Time to a Ct value of non-detectable will be examined using an exact discrete time-to-event Cox model. The analysis of correlative endpoints will be primarily descriptive and graphical in nature.

The primary test of efficacy will be one-sided and tested at level alpha=0.05. All additional tests will be two-sided and tested at level alpha=0.05.

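### Section 8.2 lets any unpowered clinical element that differs between undefined, non-randomized arms overrule the AUC primary endpoint, contradicting Sections 16.2 and 19

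*Combined protocol and SAP*

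**What the plan says.** Three parts of the document rank the efficacy endpoints, and they do not agree.

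- **Section 8.2** lists hospitalization, mechanical ventilation and death within 30 days as secondary. It opens its rule with "Although the study is not powered for the clinical endpoint" and ends it by saying that if any element "will reach statistical difference between arms, such clinical endpoint will be considered as an overruling endpoint of efficacy".
- **Sections 19.1 and 19.2.2** make the AUC of Ct the Phase IIa primary endpoint, tested against 130: "The primary test of efficacy will be one-sided and tested at level alpha=0.05". The clinical events are secondary, each tested two-sided at 0.05. There is no overruling rule and no multiplicity control.
- **Section 16.2** calls mechanical ventilation the primary efficacy endpoint, in parentheses, inside its list of secondary endpoints.

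On the comparison itself, Section 19.2.2 says only that the events up to and including "death within 30 days will be compared using Fisher's exact test", without naming the groups. The AUC part of that section does name a comparator: "In order to compare the AUC between rintatolimod versus historical institutional benchmarks". Section 19.1 describes Phase IIa as single arm and says neither cohort is randomized, Section 19.4 repeats that the trial is non-randomized, and Section 2.1 explains why there is no comparator regimen.

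**The concern.** A null AUC with one nominally significant clinical element is a negative result under Section 19.2.2 and an efficacy verdict under Section 8.2. If the Section 16.2 label is taken at face value, the answer turns on whether that element is ventilation. No section says which governs.

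Because the arms are not defined, the groups could be chosen after the data are seen, and every available contrast is non-randomized. The rule also has no direction: as worded, a significant excess of deaths on treatment would equally become the overruling efficacy endpoint.

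**Working it through.** **1. What could the arms be?**

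- *Study drug versus historical controls.* This is the best-supported reading. Section 2.6 plans historical comparison, Section 9 mentions control arms, and Section 19.2.2 defines a rintatolimod group and a control group for the AUC. All of this concerns viral load or remdesivir use. The pilot data in Section 19.3 are Ct values only, so no control counts of hospitalization, ventilation or death are given. Section 2.6 also says standard of care changes over time. The outside rates quoted (40% ventilation or death in 8.2; 28-day death of 22.9% and 25.7% in Section 9) are not a usable comparator.
- *Main versus Expansion.* This is planned nowhere but not excluded. Main excludes severe COVID-19 (3.2). Expansion is opened to more severe disease, including respiratory failure (3.3), and excludes ventilated patients only above an FIO2 of 60% (3.4). The contrast is confounded by severity.
- *Interferon tiers.* Also not excluded. At 3 versus 3 the smallest two-sided Fisher p is 0.10, so the rule cannot fire. At 6 versus 6, 0/6 against 5/6 gives p = 0.015.

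**2. Is there a figure in the plan to reproduce?** Not for these endpoints. The only stated power (0.80 at n = 10) belongs to the AUC test, and this point does not depend on it.

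**3. How easily could the rule fire without a drug effect?** This is an illustration for Main versus Expansion only. The event rates are assumptions. The Expansion size is its maximum of 20. Main is taken as 10 (Phase IIa), 34 (24 Phase I maximum + 10) or 44 (stated maximum). The method enumerates all outcomes of two independent binomials:

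P(trigger) = Σ Bin(a; n₁, p₁) · Bin(b; n₂, p₂) over tables with two-sided Fisher p ≤ 0.05.

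| Rates, Main vs Expansion | 10 vs 20 | 34 vs 20 | 44 vs 20 |
|---|---|---|---|
| 20% vs 40%, favouring Main | 13.1% | 28.2% | 33.6% |
| 10% vs 40%, favouring Main | 30.0% | 66.2% | 73.1% |
| Equal rates, 10–50%, either direction | 1.3–3.1% | 2.3–3.8% | 2.6–3.8% |
| At least one of three elements, equal rates | 3.7–9.1% | 6.6–11.1% | 7.5–10.9% |

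The last row is 1 − (1 − t)³, with t from the row above and independence assumed. The nominal bound is 1 − 0.95³ = 14.3%. With no events in Main, the smallest triggering results are 0/44 against 3/20 (p = 0.027) and 0/10 against 8/20 (p = 0.029).

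The first two rows against the third show that a difference in severity, not multiplicity, drives the risk. Direction matters as well: at equal 10% rates and 10 versus 20, about 1.25 of the 1.26 percentage points go against Main.

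**4. Is each element well defined?** Not fully. Death is counted to 30 days in 8.2 and 19.2.2, and Section 7 follows patients to Day 30. Both calendars in Appendix F follow survival only through Day 14, and their footnotes score 14-day (Main) and 15-day (Expansion) survival. Section 19.2.2 restricts hospitalization to patients not already inpatients but sets no matching restriction for ventilation, although Expansion may enrol ventilated patients.

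**The case against.** The strongest reply is that the rule has little force. With a single-arm Phase IIa and no clinical control data, the sentence looks like leftover wording from a controlled design, and no planned contrast can trigger it. The viral-load primary is stated in Sections 1.1, 8.1, 16.1 and 19.1, and the Section 16.2 label sits under a secondary heading, where it may mean only the lead clinical item. The trial is small and meant to support a later randomized one. A rule without direction also gives some protection against over-reading a surrogate when clinical outcomes go the wrong way.

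Part of this stands. The Section 16.2 label is ambiguous. The historical-control reading is an inference. The percentages size only an unplanned contrast, and they apply full cohort sizes even to hospitalization, whose denominator would be smaller. Day-30 deaths would be largely captured through serious adverse event reporting (17.7.1), so that mismatch is mainly one of wording. Losing the non-directional safeguard is a real cost.

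It does not remove the contradiction. Section 19.2.2 does plan Fisher tests of these same events, directly after defining treated and control groups, so the rule can be applied. Nothing says Section 19 prevails over 8.2. The plan also sets a formal primary test with its own alpha and power, which 8.2 would override.

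**Conclusion.** The concern holds and must be fixed before analysis. As written, Section 8.2 can replace the result of the single primary efficacy test with a non-randomized contrast on an endpoint the plan calls unpowered, and Sections 16.2 and 19 do not support that.

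This rests on the text alone. The size under the likeliest reading cannot be computed, because no historical clinical counts are given. The 13.1% to 73.1% range is illustrative: it assumes event rates, no drug effect, and a Main versus Expansion contrast that no section plans. Multiplicity is the smaller problem, and an alpha correction would not cure confounding. The survival time points and the ventilation denominator are side items on which the conclusion does not depend.

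**What to change.** 1. Delete the overruling sentence in 8.2 and the primary-efficacy label in 16.2, leaving the AUC as the only primary efficacy test.
2. In 19.2.2, report each clinical endpoint per cohort as a proportion with an exact 95% confidence interval. If the Fisher comparison stays, name its groups, label it exploratory, and give the source, dates and number of any historical controls.
3. Analyse new ventilation only in patients not ventilated at Day 1, in line with the existing restriction for hospitalization.
4. Reconcile 30-day death in Sections 7, 8.2 and 19.2.2 with the Day 14 follow-up and the 14- and 15-day survival in Appendix F.
5. State that an adverse clinical difference is weighed through safety review and reported next to the AUC result.

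**Cost.** The hierarchy changes are wording only. Keeping 30-day death needs a Day 30 vital-status entry in the Main calendar; Section 7 already commits to that follow-up, and the Expansion calendar already has a Day 30 visit. The clinical endpoints lose any confirmatory claim, and their intervals are wide: 0/10 gives 0–30.8%, 2/10 gives 2.5–55.6%, 4/20 gives 5.7–43.7%. An adverse clinical difference would no longer override a favourable AUC automatically, which is why item 5 is needed.
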